Part B: Approach-Research Design and Methods: Having completed Specific Aims 1 and 2 in the first 18 months of this grant, we now turn to implementation of a randomized controlled trial of SMDM to evaluate Specific Aim 3.

B.1. Participants:

The planned RCT sample will consist of 166 eligible patients who receive care for type 1 diabetes at any Nemours foundation entity or at the Barbara Davis Center for Childhood Diabetes in Denver, as well as a parent or other legal caregiver of each youth. Enrollment criteria for these patients include: Age, at least 11 but not yet 18 years old, T1D for ≥ 1 year or for at least 6 months and with the most recent Hemoglobin A1c of 7.5% or higher, and facing a decision about CSII or CGM. Access to technological advances in diabetes care may be limited for racial/ethnic minorities, so we will over-sample them to enroll at least 40 youth who are self-identified racial/ethnic minorities (24% of sample). See the Section on Representation of Women and Minorities for how this will be achieved. The enrollment objectives include a minimum of 30 patients facing each treatment decision to facilitate comparisons between them.

Since preparation of the Decision Aid websites has required more time than we expected, and since the funding agency (PCORI) does not now approve no-cost extensions of their funded studies, the work must end by March 31, 2016. Therefore, the duration of follow-up for each enrolled participant will depend on the date of that participant's enrollment as follows: Enrollment before 3/31/15: 12 months; Enrollment 4/1/15 through 6/30/15: 6 months. Enrollment will end on 6/30/15 and data collection will end on 12/31/15, allowing 3 months for data cleaning and verification and completion of statistical analyses. PCORI is considering allowing no-cost extensions and if that happens, the duration of follow-up for late-enrolling participants will be extended.

Enrollment criteria are:

Inclusion Criteria for Youths: Age 11 to not yet 18 years; Physician-diagnosed T1D for at least 1 year or for at least 6 months and with the most recent Hemoglobin A_{1c} of 7.5% or higher (the minimum HbA_{1c} criterion ensures that no patients will enroll in the study who have substantial remaining endogenous insulin secretion. This will preserve the opportunity to evaluate treatment effects on HbA_{1c}, which is an important secondary outcome of the study); Considered by treating HCP to be an appropriate candidate for CSII or CGM

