Recruitment Plan C: This strategy will be used in those instances in which a family is recruited remotely. The study will be advertised with a brief description of the study in the Childrenwithdiabetes.com website. The description will include a link for more information that will take them to a study flyer within REDCap. Then if they express interest in participating in this research, the informed consent and assent forms will pop up. Families will be offered the opportunity to speak with a representative of the research team if they wish to do so before signing the consent and assent forms. The document will conclude with an electronic signature process consisting of either signing with their mouse or if using a touchpad, signing with their finger. They will have an opportunity to print the forms prior to submitting them (families that are consented electronically will also have a copy of the signed consent forms emailed to them). Prior to submitting the signed consent and assent forms, the family will complete a few contact information questions, so that a research coordinator may contact them to get them started in the study. There will be other minor modifications to the study procedures for families enrolled remotely: study visits will not need to directly coincide with clinic visits therefore can disregard references to clinic visits; participant's diabetes physician will not play a role in the study (other than to inform him/her of the participant's enrollment and to ask for copies of A1cs); a diabetes educator nurse will

not be completing the SMDM Intervention Summary Form.

[figure not shown]
Childrenwithdiabetes.com also has a couple of international Friends for Life conferences a year, in which we will also try to recruit participants both in person and by having flyers distributed to attendees of the conferences (Church Falls conference April 8-10, 2016 and Orlando conference July 5-10, 2016).

Randomization Procedures: Once a given adolescent/parent dyad completes all baseline measures, they will be randomly assigned with equal probability to one of the two study conditions described below.

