Hypothesis 2: Compared to UCP, the SMDM group will have significantly more favorable status in terms of scores for treatment adherence (DSMP-SR), HbA_{1c}, and frequency of moderately severe or severe hypoglycemia at each follow-up measurement point.

Hypothesis 3: Effects of SMDM on indices of optimal use of, and satisfaction with, CSII or CGM will be mediated by changes in the measures of decision quality (Test of CSII or CGM Knowledge, Decision RegretScale, SURE Test, Decision Satisfaction Scale).

Hypothesis 4: Significant moderators of benefit from SMDM along the measured outcomes will include baseline measures of socioeconomic status, health literacy and numeracy, youth age, and family structure.

Hypothesis 5: SMDM will have indistinguishable beneficial effects on the primary study outcomes regardless of which clinical decision (CSII or CGM) was the focus of the SMDM intervention.

Statistical Power Statistical power to detect treatment effects of interest on the primary endpoints was assessed using the online DSS Research Statistical Power Calculator.¹⁷⁴ With enrollment of 166 eligible youth and parents and attrition of 10% over the 12-month study, and a resulting “Completer” sample size of 150, the study will have statistical power of .87 to detect a moderate treatment effect of ~0.4 SD on the measures of decision quality and CSII or CGM optimal use. Even though statistical power remains adequate for detection of somewhat smaller treatment effects, effects of less magnitude are unlikely to have sufficient clinical significance to warrant the added cost and inconvenience of implementing SMDM.

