A subcontract has been negotiated with Thomas Jefferson University that will cover the personnel costs (salary plus fringe benefits) for the involvement of [name]. as a co-investigator on this project. [name] would be supported for 0.6 calendar months (5% FTE) during all 3 project years. Her base salary is above the PCORI cap and is budgeted at \$200,000 annually. Fringe benefits and indirect costs are calculated per established Thomas Jefferson University policies and procedures in effect at the time of this application. The TJU indirect cost rate for such arrangements is below the 40% allowed by PCORI. This subcontract will end on December 31, 2014 as [name] and the research staff at TJU will become Nemours employees at that time.

We are establishing a subcontract with The Barbara Davis Center for Childhood Diabetes, the only freestanding pediatric diabetes treatment center in the US. Affiliated with the University of Colorado College of Medicine and Children's Hospital of Colorado, BDC manages over 3,300 pediatric patients with type 1 diabetes. A subcontract with the Barbara Davis Center would commit BDC to the recruitment of 80 eligible patients/parents between June 1 and November 30, 2015 and to maintain study follow-up over the following 12 months for each participant. The subcontract would cover the personnel costs (salary plus fringe benefits) for the involvement of [name]. as a co-investigator on this project, [name] CDE as Diabetes Nurse and [name] as Research Assistant.

Project Plan And Timeline

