Time Frame The first 9 months of funding were dedicated to planning and implementation of the QIS study and interpreting those findings for further planning of the RCT. Development of the decision aids was finalized in month 18. Concomitantly we completed preparation of a detailed study procedure manual, preparation of a detailed SMDM intervention manual, development and pilot testing of online questionnaire administration, automated scoring and data management, and the acquisition of budgeted supplies. Project staff was hired or assigned and then trained to proficiency criteria on all aspects of protocol implementation. Recruitment of participants for the RCT will begin at about month 21. If we can enroll 16 patients per month study-wide, we would reach the 166 patient target within 10 months, or at about month 27 of the grant period. Data collection will end at month 33, December 31, 2015, regardless of the length of time the last participants are in the study. This would allow 3 months for data cleaning and verification, data analysis, preparation and submission of abstracts and papers, and preparation and submission of a renewal application. The sponsor, PCORI, may allow a one-year no-cost extension if the study aims cannot be achieved within the planned 3-year award period and it is possible that we will take advantage of that opportunity.

Patient And Stakeholder Engagement Plan

Previous research on shared medical decision making shows that consumers and health professionals often have quite divergent views regarding the value they place on different elements of the structure, process and outcomes of medical decision making. Therefore, it is particularly important to obtain and utilize the varied perspectives of key stakeholders if this line of research is to yield results that resonate with all of them. This research will place major emphasis on the appropriate engagement of patients, parents and health care providers in the planning, design, implementation, analysis and interpretation of the research and its eventual results. Our engagement plan rests on several fundamental components, each of which is described in more detail below:

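### Two unreconciled calendars: the accrual sentence puts the 166th patient at month 27 instead of about month 31, and the 150 twelve-month completers behind the power statement do not fit the written cut-offs

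*Combined protocol and SAP*

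**What the plan says.** Part D, Project Plan and Timeline, gives the accrual plan: "Recruitment of participants for the RCT will begin at about month 21". At a hoped-for rate of 16 patients a month across all sites, the paragraph then expects that "we would reach the 166 patient target within 10 months, or at about month 27 of the grant period". It also ends data collection at month 33, dated December 31, 2015, however long the last participants have been in the study. It treats a one-year no-cost extension as something the funder may allow.

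B.1 Participants gives the operative dates. All work ends by March 31, 2016, and "Enrollment will end on 6/30/15 and data collection will end on 12/31/15". Follow-up depends on the enrollment date: "Enrollment before 3/31/15: 12 months", and 6 months for those enrolled from April through June 2015. B2 Study Design and the footnote to B.4 Measurement Schedule repeat that late enrollees may be followed for only 6 months unless an extension is allowed.

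Other sections use later dates. The Denver subcontract, described in the budget justification and again in Part D, Consortium/Contractual Arrangements, commits that site to "recruitment of 80 eligible patients/parents between June 1 and November 30, 2015" with 12 months of follow-up each. Recruitment Plan C in B.1 adds recruitment at two meetings ("Church Falls conference April 8-10, 2016 and Orlando conference July 5-10, 2016").

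B.5, Statistical Power, rests on 166 enrolled, "attrition of 10% over the 12-month study", and 150 completers.

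**The concern.** The start month, monthly rate, duration and finish month in one paragraph cannot all be true. The finish month is not an isolated slip, because month 27 is June 2015, the month in which B.1 closes enrollment. The written dates therefore look as if they accommodate the full sample when, at the stated rate, they do not.

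The follow-up rule has a similar defect. Patients enrolled from January through March 2015 are promised 12 months, yet data stop on 12/31/15, before any of them except a New Year's Day enrollee reaches a full year.

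Two things are at stake. The power paragraph quotes a sample size for a 12-month study that takes no account of these limits. And site staff cannot tell which enrollment close and which follow-up length apply to a given family. The Denver site alone is to supply 80 of 166 patients (48%) under dates that conflict with B.1.

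**Working it through.** **Mapping months to dates.** The protocol sets month 33 = December 2015. Hence month 21 = December 2014, month 27 = June 2015, month 31 = October 2015 and month 36 = March 2016. The last agrees with the stated end of work.

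**The plan's own figures.**
- Accrual duration: 166/16 = 10.4 months. The stated 10 months reproduces, rounded.
- Completers: 166 × 0.90 = 149.4. The stated 150 reproduces as attrition alone.
- Finish month: 21 + 10.4 = 31.4. The stated month 27 does not reproduce.
- A 10-month accrual ending at month 27 would have to start at 27 − 10 = month 17. The same paragraph finalizes the decision aids only in month 18.

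**Enrolled by each cut-off at 16 per month.** A start at about month 21 may mean early or late December 2014, so each count has two ends. Counting days instead of whole months lowers 96 and 48 by one.

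| Cut-off | Enrolling months | Enrolled | What 12/31/15 allows |
|---|---|---|---|
| 12/31/14 | 0–1 | 0–16 | full 12 months |
| 3/31/15 | 3–4 | 48–64 | at least 9 months |
| 6/30/15 | 6–7 | 96–112 | at least 6 months |

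Applying the full 10% attrition to the last two rows leaves 43–58 and 86–101.

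**Does a faster rate rescue the completer count?**
- Filling 166 by 6/30/15 needs 166/7 = 23.7 to 166/6 = 27.7 per month. Those enrolled by 3/31/15 would then number 27.7 × 3 = 83 to 23.7 × 4 = 95, or 75–85 after attrition.
- For all 166 to have even 9 months, accrual would have to finish by 3/31/15, at 166/4 = 41.5 to 166/3 = 55.3 per month.
- For all 166 to have a full 12 months, everyone would have to be enrolled within December 2014.

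So 150 completers at 12 months cannot be had from accrual spread up to the 6/30/15 close. Which patients can reach 12 months is set by the dates, not by the rate.

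**The later dates.** Denver enrollees from June through November 2015 would finish 12 months between June and November 2016, all after the 3/31/16 end of work. Both recruitment meetings also fall after that date. If a one-year extension is assumed to move data collection to 12/31/16, the month-31 target plus 12 months (October 2016) and the Denver follow-up (November 2016) both fit. A patient enrolled in July 2016 would reach 12 months in July 2017, beyond even a 3/31/17 end of work.

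**Indicative power on one consistent basis.** For a two-sided 0.05 test of 0.4 SD with n per arm, power = Φ(0.4·√(n/2) − 1.96).
- n = 75 (150 in all): 0.69 (0.68 by the t-test).
- 86–101 in all: 0.46–0.52.
- 43–58 in all: 0.26–0.33.

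The calendar effect is the fall from 0.69. The gap between 0.69 and the stated .87 exists at N = 150 and has nothing to do with dates.

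**The case against.** The strongest reply is that the protocol is open about this. It says follow-up may be truncated, it names the possible extension, and B.1 says late enrollees' follow-up will lengthen if one is allowed. The Denver and conference dates suggest that an extended calendar was in fact in use, and on such a calendar 166 patients with 12 months could largely fit. A reader might infer that the full sample and the one-year question are impossible. The documents do not support that, because it takes one of the two written calendars as the only one. What the reply leaves standing is that no section says the extension was granted, four sections still treat it as only possible, and the power paragraph reflects neither case.

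Three further limits are sound.
- The 96–112 enrolled depends on a rate that the protocol states conditionally. About 24 to 28 per month would reach 166 by the close.
- The practical-considerations table in B2 lets Visit 5 measures be taken 9 to 12 months after baseline when clinic visits depart from the usual quarterly schedule. The 48–64 early enrollees may therefore supply Visit 5 data, not only the 16.
- Truncated patients are not lost. The Full Analysis Set needs one post-baseline record, the mixed model uses partial follow-up, and B.5 assesses the primary endpoints at each post-decision visit, so most have data by Month 6. The power figures above are for simple endpoint comparisons and should not be read as the power of the mixed model.

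The Completer Analysis Set is different. It requires every post-baseline primary assessment, and a patient stopped at 6 months cannot supply those of Visit 5.

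A reader might also set the stated .87 against the lower powers and blame the whole gap on the calendar. That would be wrong, since most of the gap between .87 and 0.69 would remain with a perfect calendar.

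**Conclusion.** The point holds in this form: the protocol carries two calendars that are not reconciled, one of them contains an arithmetic error, and the completer count in B.5 matches neither the stated cut-offs nor the stated accrual. At 16 per month from month 21, the target falls at about month 31. Under the unextended dates about 96 to 112 are enrolled, at most about 16 can have a full 12 months, and about 48 to 64 can reach the Visit 5 window, against 150 completers assumed.

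These counts rest on a December 2014 start, a steady rate, and no extension. The enrolled number moves with the rate. The rule on who can reach 12 months does not. If the extension is in force, the sections that set the 6-month rule and the 2015 cut-offs are the ones that are wrong. Correction is needed in either case. Nothing here shows that the primary time point should change.

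**What to change.** Replace the dates in the budget justification (Denver subcontract), B.1, Recruitment Plan C, B2, the B.4 footnote and both relevant parts of Part D with one calendar that states whether the extension is in force.

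- **If it is:** give the new enrollment close and a data-collection end that delivers 12 months for the last enrollee, including anyone recruited at the 2016 meetings. Delete the 6-month rule.
- **If it is not:** apply the 6/30/15 close to every site. Correct the accrual sentence and restate the enrolled N. Correct the 12-month promise to those enrolled after 12/31/14. In B.5, restate expected N and power separately for Month 6 (all enrollees) and for Month 12/Visit 5 (early enrollees only).

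Do not simply change month 27 to month 31 while data still end at month 33. A patient enrolled then would have about 2 months of data and no Month 6 visit. Correct the .87 as a separate item.

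The cost is protocol wording and a recalculation, with no new data. Without an extension, the stated N and power become less favourable.

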Talking with others who are using this device or method	0	1	2	0	1	2
Talking with others who decided against this device or method	0	1	2	0	1	2
Getting more information from internet, books, workshops, etc.	0	1	2	0	1	2
Talking about this with others who I trust	0	1	2	0	1	2
Learning about the amount of work and trouble it will take	0	1	2	0	1	2

Outcome of decision making:

- Reject this option, stay with current treatment
- Put off decision to a later date
- Put off decision, try harder with current treatment
- Put off decision until a recent change in treatment can be evaluated
- Get more information, then decide
- Start using this option

Parent: How satisfied are you that you made the best decision for you?

- Very Dissatisfied
- Somewhat Dissatisfied
- Neither Satisfied Nor Dissatisfied
- Somewhat Satisfied
- Very Satisfied

Adolescent: How satisfied are you that you made the best decision for you?

- Very Dissatisfied
- Somewhat Dissatisfied
- Neither Satisfied Nor Dissatisfied
- Somewhat Satisfied
- Very Satisfied

Description of Decision Making Routines
Shared Medical Decision Making group

Decision under consideration: ___CSII ___CGM

Participants in decision making:

Patient name: _____
 Parent/caregiver name: _____
 Other: _____
 Other: _____

For each of these activities or experiences, check the number that best describes how often you did this while you were making this decision and then check the number that matches how important that was in affecting the decision you made. **Only include things that you did outside of the two video conference sessions with the Certified Diabetes Educator. This should include only the activities you would have experienced even if you weren't in this study.**

	How Often Did You Do This? 0=Never 1=Just a little 2=Quite a bit			How Much Did It Affect Your Choice? 0=Not at all 1=Just a little 2=Quite a bit		
Teaching session with diabetes educator	0	1	2	0	1	2
Chance to try out the new device or method	0	1	2	0	1	2
Seeing and touching the tools we would use	0	1	2	0	1	2
Talking with others who are using this device or method	0	1	2	0	1	2
Talking with others who decided against this device or method	0	1	2	0	1	2
Learning more from internet, books, workshops, etc.	0	1	2	0	1	2
Talking about this with others who I trust	0	1	2	0	1	2
Learning about the amount of work and trouble it will take	0	1	2	0	1	2

Outcome of decision making:

- Reject this option, stay with current treatment
- Put off decision to a later date
- Put off decision, try harder with current treatment
- Put off decision until a recent change in treatment can be evaluated
- Get more information, then decide
- Start using this option

Parent: How satisfied are you that you made the best decision for you?

- Very Dissatisfied
- Somewhat Dissatisfied
- Neither Satisfied Nor Dissatisfied
- Somewhat Satisfied
- Very Satisfied

Adolescent: How satisfied are you that you made the best decision for you?

- Very Dissatisfied
- Somewhat Dissatisfied
- Neither Satisfied Nor Dissatisfied
- Somewhat Satisfied
- Very Satisfied

Appendix 3. SMDM Intervention Summary

Shared Medical Decision Making in Pediatric Diabetes Intervention Summary for Referring Health Care Providers

Decision under consideration: ___CSII ___CGM

Session Dates: _____

Participants in SMDM intervention:

 Patient name: _____

 Parent/caregiver name: _____

 Other: _____

 Other: _____

Parent's expressed concerns:

Adolescent's expressed concerns:

Parent's perceived benefits:

Adolescent's perceived benefits:

Areas of disagreement:

Remaining educational needs: Involvement of

other supportive persons: Utilization of

supplemental educational resources:

Interactions with others who previously faced this decision:

Competence ratings:

1=Poor

2=Marginal

3=Adequate

4=Good

5=Exceptional

Adolescent

Parent

Effort with current regimen	1	2	3	4	5	1	2	3	4	5
Knowledge of option under discussion	1	2	3	4	5	1	2	3	4	5
Use of BG results	1	2	3	4	5	1	2	3	4	5
Organizational skills	1	2	3	4	5	1	2	3	4	5
Internal motivation to succeed	1	2	3	4	5	1	2	3	4	5
Clarity of goals	1	2	3	4	5	1	2	3	4	5
Anticipation of barriers	1	2	3	4	5	1	2	3	4	5
Realistic expectations	1	2	3	4	5	1	2	3	4	5
Communication and problem solving skills	1	2	3	4	5	1	2	3	4	5
Teamwork and collaboration	1	2	3	4	5	1	2	3	4	5
Level of SMDM engagement	1	2	3	4	5	1	2	3	4	5
